3.3 Study Duration, Enrollment and Number of Sites

3.3.1 Duration of Study Participation

The study duration per subject will be up to 15 months total including 12 months since randomization. The extra days are to account for interpretation of the sleep study and scheduling of subjects, including potential cancellations due to family circumstances. Of note, subjects initially randomized to placebo will be in the study for 3 months following randomization.

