 - Adrenocorticotropic hormone: Assays will be measured by a solid-phase, two-site sequential chemiluminescent immunometric assay run on an automated Siemens Immulite 1000 clinical analyzer according to the manufacturer's specifications. Blood will be collected into iced EDTA tubes and centrifuged at 4°C.
 - DHEAS
- **Infection:** Families will keep a log of all infections and illnesses.

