Side effects of NCS: The proportion of subjects with side-effects will be computed (with 95% CI). The average number of side-effects (with 95% CI) will also be computed. We do not anticipate that there will be an appreciable number of side-effects in either treatment group, but we will have excellent power to detect a meaningful difference between groups. A Fisher's exact test with a 0.050 two-sided significance level will have 84% power to detect the difference between the 50 placebo *vs* 100 NCS subjects at 3 months, if 1% of placebo *vs* 15% of NCS subjects have side-effects at 3 months. For comparison of the 45 treated *vs* 45 placebo subjects during the second 9 months of follow-up, we will have 82% power to detect a difference between 1% *vs* 20% of subjects with side-effects, respectively. In addition, the proportion of the 100 subjects initially randomized to NCS who have side-effects at any time during follow-up will be computed (with 95% CI). An exact binomial test with a nominal 0.050 two-sided significance level will have 85% power to detect an adverse event rate of 6% amongst the 100 NCS subjects at any time during follow-up (*vs* a hypothesized rate of 1%).

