8.3 Definition of an Adverse Event

An adverse event is any untoward medical occurrence in a subject who has received an intervention (drug, biologic, or other intervention). The occurrence does not necessarily have to have a causal relationship with the treatment. An AE can therefore be any unfavorable or unintended sign (including an abnormal laboratory finding, for example), symptom, or disease temporally associated with the use of a medicinal product, whether or not considered related to the medicinal product.

All AEs (including serious AEs) will be noted in the study records and on the case report form with a full description including the nature, date and time of onset, determination of non-serious versus serious, intensity (mild, moderate, severe), duration, causality, and outcome of the event.

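### The any-time adverse event rate on NCS is tested against a fixed, unsourced 1% with no concurrent control, and the plan's own placebo assumptions imply a background nearer 2%

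*Combined protocol and SAP*

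**What the plan says.** The side-effects paragraph of section 6.4 (Combined protocol and SAP) contains three power statements.

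- A Fisher's exact test at 3 months, 50 placebo against 100 NCS children: 84% power for 1% against 15%.
- A comparison of 45 against 45 children over the second 9 months: 82% power for 1% against 20%.
- A supplementary analysis in the group first assigned to NCS. The proportion of "the 100 subjects initially randomized to NCS who have side-effects at any time during follow-up will be computed" with a 95% CI, and then: "An exact binomial test with a nominal 0.050 two-sided significance level will have 85% power to detect an adverse event rate of 6" percent, "amongst the 100 NCS subjects at any time during follow-up", against "a hypothesized rate of 1" percent.

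No source is given for the 1%. The paragraph speaks of side-effects, which it does not define, until the last test, which speaks of an adverse event rate. Section 8.3 defines the latter broadly: "An adverse event is any untoward medical occurrence in a subject who has received an intervention", and "The occurrence does not necessarily have to have a causal relationship with the treatment". Section 5.1.5 adds, under Infection: "Families will keep a log of all infections and illnesses".

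Two design features matter here. Under section 3.3.1, "subjects initially randomized to placebo will be in the study for 3 months following randomization". Under section 3.1.4, half of the initial NCS group is switched to placebo for the last 9 months.

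**The concern.** A one-sample test against a fixed rate says something about the drug only if that rate is what would be seen without the drug. Here the reference is unsourced, and no never-treated group is followed over the same window, because the initial placebo arm leaves at month 3. The numerator is open too: on the section 8.3 definition it includes events of any cause. The count also runs through 9 months in which half of the children take placebo.

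The same 1% serves for 3 months, for the next 9 months, and for the whole of follow-up. Those three uses agree only if the same children are affected in both periods.

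Side-effects of chronic NCS use are a secondary objective (section 2). A small p-value from this test could be reported as evidence of drug harm when it shows only that the combined background and drug rate exceeds 1%.

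**Working it through.** **Inputs.** From section 6.4: n = 100, null rate 1%, alternative 6%, two-sided 0.05, stated power 85%; assumed placebo rates of 1% to month 3 and 1% in the next 9 months. For the second period I read the 1% as the placebo figure, matching the 3-month sentence; the word order in section 6.4, taken literally, attaches it to the treated group. Not in the documents: any observed background rate. Rates of 3%, 5% and 10% below are assumptions.

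**1. Rejection rule.** With X the number of affected children, P(X ≥ r | p) = 1 − Σ C(100,k) p^k (1−p)^(100−k), summed over k = 0 to r−1.

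- At p = 0.01: P(X ≥ 3) = 0.079 and P(X ≥ 4) = 0.018.
- P(X = 0) = 0.99^100 = 0.366, so there is no lower rejection region.
- The test therefore rejects at 4 or more of 100, with actual size 1.8%.

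**2. The plan's power.** P(X ≥ 4 | 0.06) = 0.857, against 85% stated. It reproduces. With the 90 children expected to be evaluable at 12 months (45 per group), the cut-off is still 4 and power is 79.5%.

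**3. Background implied by the plan itself.**

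- If events in the two periods are independent: 1 − 0.99 × 0.99 = 0.0199. P(X ≥ 4 | 0.0199) = 0.139.
- If no child is affected in both periods: 0.01 + 0.01 = 0.02. P(X ≥ 4 | 0.02) = 0.141.
- If exactly the same children are affected in both: 0.01, and the probability stays at 0.018.

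On the plan's own figures the chance of a significant excess with no drug effect is thus 1.8% to 14%, and 14% under independence.

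**4. Sensitivity to the background rate, no drug effect.**

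| Any-time background | P(4 or more of 100) |
|---|---|
| 1% | 1.8% |
| 2% | 14% |
| 3% (assumed) | 35% |
| 5% (assumed) | 74% |
| 10% (assumed) | 99% |

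**5. The randomized comparisons.** Full enumeration gives 85.4% power at 3 months (stated 84%) and 82.1% for the later period (stated 82%). With equal rates of 1%, 5%, 10% and 20% in both arms, the 3-month Fisher test rejects 0.6%, 2.8%, 3.3% and 4.0% of the time. It holds its level whatever the background. Its power for 1% against 6% is only about 9%.

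**The case against.** Four points can be made for the plan.

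**The endpoint may be narrow.** The paragraph is about side effects of NCS, section 8.3 records causality for each event, and section 6.3.4 summarizes events by relationship to study drug. Section 8.11.2 describes the fluticasone risks it lists as infrequent at the dose used. If only drug-attributed events count, a low reference rate is coherent. Nor does any section say that each entry in the infection log enters this proportion. This stands, and it is why the larger false-signal figures are conditional. But section 6.4 does not say which events count, so the reader cannot tell which case applies.

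**Most of the remedy is already planned.** The confidence interval and both randomized comparisons are in section 6.4, and section 6.3.4 names exact intervals and no one-sample test. This also stands. What remains is one supplementary test and its power figure.

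**Deletion has a price.** The test carries the only stated power for a rate as low as 6%, and the 3-month comparison has about 9% power for 1% against 6%. True, but the 85% depends on treating the background as known to be 1%.

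**Little hangs on it.** The test supports no primary claim and no stated decision rule, and the DSMB receives reports by treatment arm (section 8.11.1). This limits the weight of the point.

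A reader might go further and infer that ordinary childhood illness is bound to make the test significant. The documents do not support that: they give no background rate, and at exactly 1% the test rejects 1.8% of the time. Nor do they support saying that safety has no control group, since the lack of a control applies to this test alone.

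**Conclusion.** The 85% is correct arithmetic for a test that cannot separate drug effect from background. It is reliable only if the any-time background rate is about 1%. The plan's own placebo assumptions, taken as independent, put that rate at about 2% and the false-signal chance at 14%, against a nominal 5%. If events are counted regardless of cause the chance could be much higher; if only drug-attributed events count it could stay near the nominal level or below. The size of the problem therefore depends on an event definition that section 6.4 leaves open. This is a weakness in a supplementary analysis, worth correcting because the correction costs almost nothing; it does not touch the primary analysis.

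**What to change.** In the side-effects paragraph of section 6.4:

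1. Delete the exact binomial test against 1% and its 85% power.
2. Keep the any-time proportion in the initial NCS group, with its exact 95% CI, labelled as descriptive. Say that half of these children take placebo after month 3 and that the interval is not to be read against 1%. This needs saying: 4 of 100 gives an interval of 1.1% to 9.9%, which already excludes 1%.
3. State one event definition and use it throughout the paragraph: either all adverse events under section 8.3, or those judged related to study drug, with the relationship categories that count.
4. Base inference about NCS harm on the two randomized comparisons, NCS against placebo to month 3 and continued NCS against switched to placebo in months 3 to 12. Report each as a risk difference with 95% CI beside the planned test.
5. State the limits. These comparisons are powered for 1% against 15% and 1% against 20%; the 3-month test has about 9% power for 1% against 6%; and in the later comparison both groups have already had 3 months of NCS, so there is no never-exposed control.

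The cost is a change of wording and the loss of one test with its power figure. No further data or children are needed.

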6.5 Interim Analysis

There will not be an interim analysis as this study does not involve a life-threatening condition or a life-threatening outcome.

7 STUDY MEDICATION (STUDY DEVICE OR OTHER STUDY INTERVENTION)

7.1 Study Drug Description

7.1.1 Packaging

Clinical supply description

For this study, the Investigational Drug Service (IDS) at the University of Pennsylvania will prepare blinded nasal spray bottles with a metered pump (to deliver 55 mcg/0.1 mL of fluticasone) with a 30 day supply of solution per bottle. The IDS will obtain the fluticasone from Hi-Tech Pharmacal. The IDS will purchase all supplies, gas-sterilize pumps/bottles, fill solutions under sterile conditions and dispense in 3-month increments labeled for individual study subjects.

7.1.2 Labeling

IDS will label the bottles of fluticasone and placebo. Both bottles will look identical.

7.1.3 Dosing

Fluticasone will be taken at bedtime. One squirt in each nostril will be administered by caregivers.

7.1.4 Treatment Compliance and Adherence

Compliance will be assessed by weighing medication canisters at each visit.

7.1.5 Drug Accountability

Adequate records of study drug receipt and disposition will be maintained by the Investigational Drug Service at Penn. Records of receipts, investigational drug orders, dispensing records, and disposition forms will be examined during the course of the study. The purpose of these records is to ensure regulatory authorities and the Sponsor that the drug will not be distributed to any person who is not a study subject under the terms and conditions set forth in this protocol. The study medication is to be prescribed by the Investigator or designee and may not be used for any purpose other than that described in this protocol. At study completion, all drug supplies including partially used and empty containers must be returned to Sponsor or designee.

7.2 Placebo Description

7.2.1 Packaging

Clinical supply description

The IDS at the University of Pennsylvania will prepare blinded nasal spray bottles with a metered pump to deliver placebo/0.1 mL per pump, with a 30 day supply of solution per bottle. The bottle will be amber (same as the drug bottle). The placebo will contain the following:

- Bacteriostatic Saline (Sodium Chloride 0.9% with 0.1% Sodium Benzoate) 98.9%
- Polysorbate 20, NF 1%
- Geranyl Acetate 0.1%

The polysorbate and geranyl acetate are to prove the same floral smell as the fluticasone. Polysorbate 20, NF is a pharmaceutical grade emulsifier suitable for use in oral or topical solutions; it is used to solubilize insoluble oils into water. Geranyl Acetate is one of the natural components in rose petals that helps produce the natural 'scent' of a rose. Geranyl Acetate is a component in some chewing gums and candies, in proportions similar to or larger than what will be used in this solution. Additionally, the mixture will be passed through a sterilizing filter during preparation. The IDS will purchase all supplies, gas-sterilize pumps/bottles, fill solutions under sterile conditions and dispense in 3-month increments labeled for individual study subjects.

7.2.2 Labeling

IDS will label the bottles of fluticasone and placebo. Both bottles will look identical.

7.2.3 Dosing

Placebo will be taken at bedtime. One squirt in each nostril will be administered by caregivers.

7.2.4 Treatment Compliance and Adherence

Compliance will be assessed by weighing medication canisters at each visit.

7.2.5 Drug Accountability

Same as 7.1.5.

8 SAFETY MANAGEMENT

8.1 Clinical Adverse Events

Clinical adverse events (AEs) will be monitored throughout the study.

8.2 Adverse Event Reporting

Unanticipated problems related to the research involving risks to subjects or others that occur during the course of this study (including SAEs) will be reported to the IRB in accordance with CHOP IRB SOP 408: Unanticipated Problems Involving Risks to Subjects. AEs that are not serious but that are notable and could involve risks to subjects will be

summarized in narrative or other format and submitted to the IRB at the time of continuing review.

8.3 Definition of an Adverse Event

An adverse event is any untoward medical occurrence in a subject who has received an intervention (drug, biologic, or other intervention). The occurrence does not necessarily have to have a causal relationship with the treatment. An AE can therefore be any unfavorable or unintended sign (including an abnormal laboratory finding, for example), symptom, or disease temporally associated with the use of a medicinal product, whether or not considered related to the medicinal product.

All AEs (including serious AEs) will be noted in the study records and on the case report form with a full description including the nature, date and time of onset, determination of non-serious versus serious, intensity (mild, moderate, severe), duration, causality, and outcome of the event.

8.4 Definition of a Serious Adverse Event (SAE)

An SAE is any adverse drug experience occurring at any dose that results in any of the following outcomes:

- death
- a life-threatening event (at risk of death at the time of the event)
- requires inpatient hospitalization or prolongation of existing hospitalization
- a persistent or significant disability/incapacity or
- a congenital anomaly/birth defect in the offspring of a subject.

Important medical events that may not result in death, be life-threatening, or require hospitalization may be considered a serious adverse drug event when, based upon appropriate medical judgment, they may jeopardize the subject and may require medical or surgical intervention to prevent one of the outcomes listed in this definition.

A distinction should be drawn between serious and severe AEs. A severe AE is a major event of its type. A severe AE does not necessarily need to be considered serious. For example, nausea which persists for several hours may be considered severe nausea, but would not be an SAE. On the other hand, a stroke that results in only a limited degree of disability may be considered a mild stroke, but would be an SAE.

8.4.1 Relationship of SAE to study drug or other intervention

The relationship of each SAE to the study intervention should be characterized using one of the following terms in accordance with CHOP IRB Guidelines: definitely, probably, possibly, unlikely or unrelated.

8.5 IRB/IEC Notification of SAEs and Other Unanticipated Problems

The Investigator will promptly notify the IRB of all on-site unanticipated, serious Adverse Events that are related to the research activity. Other unanticipated problems related to the research involving risk to subjects or others will also be reported promptly. Written reports will be filed using the eIRB system and in accordance with the timeline below. External SAEs that are both unexpected and related to the study intervention will be reported promptly after the investigator receives the report.

Type of Unanticipated Problem	Initial Notification (Phone, Email, Fax)	Written Report
Internal (on-site) SAEs Death or Life Threatening	24 hours	Within 2 calendar days
Internal (on-site) SAEs All other SAEs	7 days	Within 7 business days
Unanticipated Problems Related to Research	7 days	Within 7 business days
All other AEs	N/A	Brief Summary of important AEs may be reported at time of continuing review

8.5.1 Follow-up report

If an SAE has not resolved at the time of the initial report and new information arises that changes the investigator's assessment of the event, a follow-up report including all relevant new or reassessed information (e.g., concomitant medication, medical history) should be submitted to the IRB. The investigator is responsible for ensuring that all SAE are followed until either resolved or stable.

8.6 Investigator Reporting of a Serious Adverse Event to Sponsor

N/A

8.7 Medical Emergencies

Medical emergencies are very unlikely to occur in this minor increase over minimal risk study. The PI will be notified in the case of medical emergencies and participants will be referred to the nearest Emergency Department for clinical care.

STUDY ADMINISTRATION

8.8 Treatment Assignment Methods

8.8.1 Randomization

A blocked randomization scheme (with block sizes that vary randomly between 2 and 4) will be employed to initially randomize subjects to NCS or placebo at baseline; the same approach will then be employed for the re-randomization at 3 months, when the subjects

who were initially randomized to receive NCS will be re-randomized in equal numbers to receive NCS or placebo. An exception for this randomization schedule will be siblings. Specifically, siblings will be randomized to the same arm to avoid parental confusion with study drug administration. For example, parents may confuse study drug with placebo because both study drug and placebo look, taste and smell identical and parents may give the wrong medication to their children. The randomization will be stratified according to atopy/asthma, current use of inhaled corticosteroids for asthma (yes/no), obesity status and seasonality (spring/summer *vs* autumn/winter). Programs will be written in Stata to conduct the randomization, and the assignments will be stored in sealed envelopes stored in a locked cabinet that is only accessible to CTSA staff who are not affiliated with other aspects of the study.

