Statistical And Analytic Plan	
 • It is assumed that 50% of subjects will fail the baseline screening PSG. Thus, 318 subjects will be recruited initially. • 159 eligible subjects will be randomized in a 2:1 fashion to NCS vs. placebo, respectively; the initial group sizes will therefore be 106 NCS vs. 53 placebo subjects. The 2:1 randomization ratio is to allow for further randomization during the follow-up phase of the study. Based on our past studies we will assume a drop-out rate of 5% at 3 months. Therefore, the available sample size for analysis for Aim 1 will be 100 NCS vs. 50 placebo subjects. • All analyses will be conducted with Stata 13.0, with two-sided tests of hypotheses and a p-value < 0.05 as the criterion for statistical significance. • Analyses will be conducted according to the intent to treat principle, with subjects analyzed according to their initial treatment assignment. • Descriptive analyses will include computation of means (with 95% confidence intervals), standard deviations, medians, interquartile-ranges (IQR) of continuous variables and tabulation of categorical variables. • A two-group t-test for independent samples or Wilcoxon rank sum test will be used to test the primary hypothesis that

the changes in AHI are equal between the two treatment groups.

[figure not shown]
DATA AND SAFETY MONITORING PLAN

Participants' data will be closely monitored by an external Data Safety Monitoring Board (DSMB) and an external safety officer. They will monitor adverse events and treatment failures.

TABLE 1: SCHEDULE OF STUDY PROCEDURES

Percutaneous skin allergy test		X												
Blood tests		X			X									X
Ophthalmology exam		X			X									X
Nasal secretion testing		X			X									X
DXA scan		X			X									X
Urine pregnancy test		X			X									X
Randomization		X			X									
Dispense Study Drug		X			X									
Drug Compliance					X		X				X			X
Adverse Event Assessment		X	X	X	X	X	X	X	X	X	X	X	X	X

FIGURE 1: STUDY DIAGRAM

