6.3.2 Efficacy Analysis

The primary analysis will be based on an intention to treat approach and will include all subjects randomized at Visit 1.

The primary efficacy endpoint will be the change in AHI between Randomization and Visit 2.

Secondary endpoints will include the change in AHI at the 12-month visit in each group and the change in knee height, bone health, adrenal suppression, ocular health and infection at 12 months.

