6.4 Sample Size and Power

Sample size for primary endpoint:

All sample size calculations were conducted using nQuery Advisor software. It is assumed that 50% of subjects will fail the baseline screening PSG. Thus, 318 subjects will be recruited initially. 159 eligible subjects will be randomized in a 2:1 fashion to NCS *vs* placebo, respectively; the initial group sizes will therefore be 106 NCS *vs* 53 placebo subjects. The 2:1 randomization ratio is to allow for further randomization for Aim 3. Based on our past studies (see *Preliminary Data*), we will assume a drop-out rate of 5% at 3-months. Therefore, the available sample size for the primary endpoint analysis will be 100 NCS *vs* 50 placebo subjects. This is powered on a comparison of mean changes in AHI between NCS *vs* control subjects at 3-months, based on two prior studies (13, 15). The effect-size for the difference in mean changes between treatment groups for the Brouillette study, calculated as the absolute value of the difference in group means, divided by the pooled estimate of the SD of changes, was 0.87 (15), and for the Kheirandish-Gozal study was 1.75.(13) A two group t-test with a 0.050 two-sided significance level will have $\geq 99\%$ power to detect the effect size of 0.865 (observed in (13)) when the sample sizes in the two groups are 100 and 50, respectively. In addition, the two group t-test will also have $>99\%$ power to detect the effect size of 1.75 that was observed in (15). We will therefore have excellent power to determine treatment group differences of the magnitude observed by these past studies. However, as the effect sizes were so different for these two studies, and as the current study will include a more heterogeneous population, e.g., children with more severe OSAS, the observed effect-size may be smaller. If so, we will have 81% power to detect an effect size of 0.50. An effect-size of 0.50 corresponds to a mean reduction in AHI of 4.2/hr in the NCS group and no change in the placebo group, assuming the SD of changes is 8.4 (as observed in (13)); and an AHI reduction of 1/hr with NCS (and no change in placebo) if the SD of change is 2 as observed in (15). Any smaller difference between groups with respect to changes in AHI would not be clinically meaningful. We are therefore well-powered to detect meaningful changes for the primary endpoint.

Sample size for secondary endpoints:

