Comparison of the changes in AHI at 12 months: For this endpoint, the 100 remaining NCS subjects (assuming there were ~6 dropouts) at 3-months will be re-randomized in equal numbers to continued NCS or placebo. Assuming a conservative drop-out rate of 10%, there will be 45 evaluable subjects per treatment group at 12 months. We anticipate that subjects treated with NCS will continue to improve (i.e., have continued reductions in AHI), while those on placebo will have a worsening of their condition (i.e., increases in AHI). We anticipate that subjects who continue on NCS will have similar (or greater) improvements during the additional 9 months of follow-up as were observed during the first 3 months of treatment. Assuming that NCS subjects have a mean reduction in AHI of 4/hr, while placebo subjects have a mean increase of 3/hr, a two-sample t-test will have 97% power to detect this difference, assuming that the common SD of changes is 8.4 (as in (15)); if the SD of changes is 2.0 (as in (13)), then we will have >99% power. However, if the observed differences of the current study are smaller, a sample size of 45 in each group will have 80% power to detect an effect size of 0.597; this would be observed if the mean reduction in AHI is 2.4/hr for subjects treated with NCS, *vs* no change for subjects treated with placebo, assuming a SD of 4.0(13).

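### Siblings share an arm but the primary test treats children as independent: taken alone this shrinks the standard error slightly, while the net effect, with stratification also ignored, is not established

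*Combined protocol and SAP*

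**What the plan says.** Section 8.8.1 describes blocked, stratified randomisation at baseline and again at month 3. It then adds: "An exception for this randomization schedule will be siblings". The rule is explicit: "Specifically, siblings will be randomized to the same arm to avoid parental confusion with study drug administration". The reason given is that "parents may give the wrong medication to their children", so the sponsor expects that some families may enrol more than one child. Nothing in sections 3.4.1 or 3.4.2 prevents this. Section 3.2 gives the same randomisation text without the sibling exception.

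The Statistical and Analytic Plan in the synopsis names the primary test of change in AHI: "A two-group t-test for independent samples or Wilcoxon rank sum test". Section 6.3.2 sets the population: "The primary analysis will be based on an intention to treat approach and will include all subjects randomized at Visit 1". Section 6.4 uses two-group t-tests throughout for the main AHI comparisons. For the primary endpoint, with 100 and 50 children, it says: "If so, we will have 81% power to detect an effect size of 0.50". For 12 months it says that "a sample size of 45 in each group will have 80% power to detect an effect size of 0.597". Section 6 contains no family term, clustered variance, design effect or one-child-per-family rule. It also names no adjustment for the four stratification factors (atopy/asthma, inhaled corticosteroid use, obesity, season).

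**The concern.** For a family with two enrolled children, the family is the unit of allocation. Siblings share genes, home and season, so their AHI changes may well be positively correlated. Had siblings been allocated separately, some pairs would be split between arms and the correlation would partly cancel in the treatment difference. The same-arm rule removes that cancellation, and an independent-samples test then counts two related children as two full units of information. The rank sum alternative makes the same assumption.

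At stake is the calibration of the primary p-value and confidence interval. The difference in mean change is not biased by this. The stated analysis does not follow the stated allocation, and without a recorded family identifier the mismatch may be hard to repair later.

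**Working it through.** **Inputs from the documents (section 6.4).** 100 NCS and 50 placebo children analysed, two-sided 0.05, effect size 0.50, stated power 81%.

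**Assumed inputs (not in the documents).** Share *f* of children who belong to same-arm pairs, equal in both arms; within-pair correlation ICC of AHI change. Range used: *f* = 5–10%, ICC = 0.2–0.5. In 150 children this is 7.5 to 15 children, roughly 4 to 8 pairs.

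**1. The plan's own figure.** Noncentrality = 0.50 / √(1/100 + 1/50) = 0.50 / 0.1732 = 2.887, with 148 df. Power from the noncentral t is 81.8%. The stated 81% reproduces.

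**2. Sibling effect alone.** For pairs, the variance of the treatment difference is multiplied by D = 1 + *f* × ICC. The actual error rate of the nominal 5% test is 2 × [1 − T₁₄₈(1.976 / √D)]. Power with the correct standard error uses noncentrality 2.887 / √D.

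| *f* | ICC | D | SE too small by | Error rate | Power at 0.50 |
|---|---|---|---|---|---|
| 0 | – | 1.000 | 0% | 5.0% | 81.8% |
| 5% | 0.2 | 1.010 | 0.5% | 5.1% | 81.4% |
| 5% | 0.5 | 1.025 | 1.2% | 5.3% | 80.9% |
| 10% | 0.2 | 1.020 | 1.0% | 5.2% | 81.1% |
| 10% | 0.5 | 1.050 | 2.4% | 5.6% | 79.9% |

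Simulation of the t-test (200,000 trials per cell) agrees: 0.0513 and 0.0520 for 4 pairs at ICC 0.2 and 0.5; 0.0520 and 0.0566 for 8 pairs.

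**3. Sibling effect together with stratification.** Stratified allocation balances the strata between arms, so the true variance of the difference falls if the strata are prognostic. The unadjusted t-test does not use that reduction and is then conservative. Two simulations of 150 children used 16 strata (four two-level factors), 2:1 blocks of 3, 8 same-arm pairs and ICC 0.5. The block size and the share of variance in AHI change explained by the strata are assumptions. Error rate of the plain t-test:

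| Variance explained by strata | First simulation | Second simulation |
|---|---|---|
| 0% | 0.058 | 0.056 |
| 5% | 0.049 | 0.053 |
| 10% | 0.044 | 0.047 |

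The second used 20,000 trials per cell (Monte Carlo standard error about 0.0015). It also gave 0.040 with no pairs and 10% explained, and 0.046 with 4 pairs, ICC 0.2 and 5% explained. Modest prognostic strata are therefore enough to offset the sibling effect even at the upper end of the assumed range.

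**4. Twelve months (45 vs 45), only if siblings also stay together at month 3.** The stated 80% power at 0.597 reproduces (80.0%). With 2–4 pairs and ICC 0.2–0.5, the t-test error rate is 0.051–0.056 and power with a small-sample-corrected clustered standard error is 79.5–78.2%, before any allowance for stratification.

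**The case against.** The strongest counter-argument is that the sibling effect cannot be read in isolation. A reader might infer that the primary p-value and interval will be too optimistic whenever siblings enrol. The documents do not support that. The same unadjusted test ignores stratification on factors that the plan itself treats as possible modifiers of response (sections 1.5 and 6.4), and this pushes the error rate the other way. The plan gives no figure for either force, so the net sign is unknown. This objection stands.

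A reader might also infer a large effect by supposing that 20–30% of children come in pairs. Nothing supports such shares. Each sibling must separately be aged 5–12, snore habitually, meet the polysomnographic limits and pass sixteen exclusions, and the plan says of screening: "It is assumed that 50% of subjects will fail the baseline screening PSG". That figure is not specific to siblings, but it points to few pairs.

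Section 3.2's silence can fairly be called an editorial omission, since 8.8.1 supplies the rule. Coverage of month 3 is less clear: the exception follows directly on the sentence describing both randomisations, which suggests that it applies to both, but the text does not say so.

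What survives is the mismatch itself. Allocation is partly by family and also stratified, while the named analysis reflects neither.

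**Conclusion.** The point holds as a minor one. Siblings are kept in one arm, more than one child per family may enrol, and the primary test and power figures assume independent children. The sibling component alone makes the standard error 0.5–2.4% too small, under the assumptions of 5–10% of children in pairs and ICC 0.2–0.5. It is zero if no siblings enrol or their changes are uncorrelated.

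It is not shown that the primary test is anti-conservative overall. Nor is the stated 81% power an error: it is correct under independence and, over the assumed range, changes by about two points at most. The same-arm rule has a sensible practical reason and need not change.

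**What to change.** - **Data:** add a family identifier to the case report form.
- **Section 6.3.2:** specify that the difference in mean change in AHI is estimated by linear regression on treatment, with the randomisation stratification factors as covariates and family-clustered standard errors with a small-sample correction (for example CR2 with Satterthwaite degrees of freedom). Clustering alone would leave the stratification mismatch in place.
- **Sensitivity analysis:** keep only the first-enrolled child per family. This also serves if the rank sum test is used.
- **Sections 3.2 and 8.8.1:** state the sibling exception in both, and say whether it covers the month-3 re-randomisation. If it does, handle families in the same way in the 12-month comparison.

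**Cost.** One data field and a few sentences, best settled before treatment comparisons are seen. In simulations without covariates, the corrected clustered interval was about 0.3% wider than the t-test's with no siblings and 0.8–3.2% wider with 4–8 pairs. Its error rate was 0.0495–0.0505 over those scenarios, and power was 81.8% with no pairs and 81.1–79.4% with 4–8 pairs. With covariates the estimate need no longer equal the raw difference in means, which should also be reported. The one-child analysis loses a little power: 4 pairs leave 97 vs 49 (about 81%); 8 pairs leave 95 vs 47, giving noncentrality 0.50 / √(1/95 + 1/47) = 2.80 and power of about 79.5%. If very few siblings enrol, there is little gain.
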